The purpose of this initial analysis is to characterize the treatment patterns and treatment duration of adult patients with advanced and metastatic RCC across various real world claims databases (Truven, Optum and Pharmetrics claims). Treatment patterns for these various US population based claims dataset will be assessed for consistency and regimen-specific population differences, as well as assessing feasibility for sub-analyses.

In order to isolate lines of therapy of interest, all medications used for advanced RCC must be considered. Thus, lines of therapy will be performed considering the following RCC medications (see [Table 4](#)):

PFIZER CONFIDENTIAL

Table 4. Medications of Interest

Drug Class	Ingredient	Brand Name	Dosage Form	Mechanism
TKI	Pazopanib	Votrient	Oral	Tyrosine Kinases Inhibitor
TKI	Sunitinib	Sutent	Oral	Multiple receptor tyrosine kinases (RTKs)
TKI	Axitinib	Inlyta	Oral	Kinase inhibitor
TKI	Cabozantinib	Cabometyx/Cometriq	Oral	New Novel TKI
TKI	Sorafenib	Nexavar	Oral	Multikinase inhibitor
TKI	Levantinib	Lenvima	Oral	RTK inhibitor
TKI	Erlotinib	Tarceva	Oral	Epidermal Growth Factor Receptor tyrosine kinase inhibitor
mTOR	Temsirolimus	Torisel	Both oral and IV	Inhibitor of mammalian target of rapamycin
mTOR	Everolimus	Afinitor	Both oral and IV	Mammalian target of rapamycin inhibitor
IO	Ipilimumab	Yervoy	Injection	Human cytotoxic T-lymphocyte antigen 4 (CTLA-4)-blocking antibody
IO	Nivolumab	Opdivo	Injection	Checkpoint monoclonal Antibody PD-1 Inhibitor
IO	Atezolizumab	Tecentriq	Injection	Checkpoint monoclonal Antibody PD-L1 Inhibitor
IO	Durvalumab	Imfinzi	Injection	Checkpoint monoclonal Antibody PD-L1 Inhibitor
IO	Pembrolizumab	Keytruda	Injection	Checkpoint monoclonal Antibody PD-1 Inhibitor
IO	Avelumab	Bavencio	Injection	Checkpoint monoclonal Antibody PD-L1 Inhibitor
IO	Bevacizumab	Avastin	Injection	Recombinant monoclonal antibody VEGF/VEGFR Inhibitor

First-line and subsequent lines (up to 3) of monotherapy and combo-therapy regimens for aRCC patients will be identified and the following metrics will be considered for first-line of therapy:

- Time from first ever metastatic diagnosis to first line regimen;
- Duration of first line therapy;
- Patterns of switching, augmentation and discontinuation;
- Treatment interruptions.

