Treated Period Follow-Up. Patients will be followed over the period treated with advanced RCC therapy. Time treated will be defined as the time from the index date to the date of the end of the last advanced metastatic RCC prescription (end of supply for orals/administration date plus 30 days for injectables), end of enrollment, end of follow up, or death (see more specifics on oral versus injectable rules in [6.3.1 Variables](#) section of this protocol).

Analysis 2. Describe various treated populations of interest by demographics, clinical characteristics, as well as cost and utilization

Describe the demographics and other baseline characteristics of the first-line treated cohorts of interest identified in the treatment patterns analysis (Analysis 1) for RCC patient as follows:

Baseline Characteristics (see [6.3.2 Baseline Characteristics](#)):

- Age at index;
- Gender;
- Race;
- Region;

PFIZER CONFIDENTIAL

- Payor;
- Clinical characteristics: Quan-Charlson Comorbidity Index (CCI) scores and baseline comorbidities;
- Prior treatment (6 months prior) - nephrectomy, radiation/ablation, interferon, high-dose interleukin-2, other anti-neoplastic medications;
- Secondary malignancy locations (6 months prior);
- Baseline costs of care (6 months prior);
- Baseline health care resource utilization (6 months prior).

Analysis 3: Evaluate the key outcomes of interest for advanced RCC therapy regimens toward demonstrating existing unmet needs in RCC given currently available therapies (eg, ipilimumab/nivolumab).

Treatment duration, discontinuation, interruption, switching and therapy augmentation will be presented, as will the burden of disease costs and health care utilization. Survival will also be explored, although regimens are too new for extensive follow-up time.

Overall Outcomes Study Period. For the outcomes analysis, follow-up will be defined as the time from the index date to the end of specified follow up period of 6 months, end of enrollment, or death. Follow-up may vary given sample sizes of study population, with by subanalysis using 1-year or 2-years of follow-up time from study index date for certain sub-populations.

Outcomes include:

- **Time to Treatment Failure (TTF)** – First line time to treatment failure (TTF) is defined as the time from first-line therapy start to treatment discontinuation for any reason, including switched, augmented therapy, end of enrollment, death.

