6.2.1. Inclusion Criteria

Subjects will be selected irrespective of their survival status. Patients must meet all of the following inclusion criteria to be eligible for inclusion in the study:

- **Index date:** The first prescription or administration of one of the medications indicated for advanced RCC recorded in the database between April 2018-March 31, 2019, among those with no aRCC treatment in their history.
- Age 18 years or older in the year of the index first line therapy prescription.
- 2 or more RCC diagnoses (ICD-9: 189.0; ICD-10: C64.1, C64.2, C64.9) at least 30 days apart, in the 1 year prior to the index date until 30 days post index date.

PFIZER CONFIDENTIAL

- 2 or more code for secondary malignancy codes indicating possible diagnoses for metastatic disease at least 30 days apart, in the 1 year prior to the index date until 30 days post index date. (ICD-9: xx-199.xx; ICD-10: C77-C79, except ICD9: 198.0 Secondary malignant neoplasm of the kidney and ICD10: C79.0 Secondary malignant neoplasm of the kidney and renal pelvis).
 - CCI [REDACTED]
- Continuous enrollment from 12 months prior to the index date. Patients will be required to have continuous enrollment from their index date until the end of the available data. This will allow for sub-analysis of cohorts with 3 months, 6 months and 12 months of available data.

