6.3. Variables

6.3.1. Treatment Pattern Variables

Table 5. Treatment Pattern Variables

Variable	Operational definition
Initial (1L)Treatment Regimen	The first treatment regimen prescribed following a primary and secondary diagnosis of advanced/metastatic disease.
Monotherapy vs Combo therapy	Categorical: Yes/No Combo therapy is defined by a second medication filled on or within 30 days of the original medication and the original medication is filled subsequently. CCI [REDACTED]
Time to FL treatment received	Continuous: days Length of time (days) from the first mRCC diagnosis (first ever secondary malignancy code associated with RCC) to first line therapy prescription.
Treatment discontinuation date (by LoT) – to be used for time to treatment failure (TTF) and time to next line of therapy	Date Treatment discontinuation indicating the end of LOT will be identified as the earliest of: 
For oral therapy: to the run-out date of the last prescription (ie, date of last prescription plus days supply) in the same treatment line.For non-oral therapy: 30 days after the last observed prescription/administration prior to at least a 30 day gap in therapy of all agents included in the first line of therapy.1 day before a new prescription/administration date, whichever occurred earlier.For multiple drug regimens: the above would be triggered by the last prescription/administration in the regimen.Death.End of enrollment.
Days of continuous treatment (by LoT)	Continuous: days The duration of each LOT will be measured from the first prescription or administration of line of therapy medication(s) to the end of the line of therapy, allowing for 30 day allowable gaps in therapy.
Treatment Continuation	Categorical (Y/N) There is no >30 day gap (ie, persistent treatment) for the index medication during follow-up period.

PFIZER CONFIDENTIAL

[REDACTED]

Variable	Operational definition
Treatment Interruption	Categorical (Y/N) At least one instance of >30 day gap (ie, non-persistent treatment) for the index medication during follow-up period or LOT followed by resuming therapy (not mutually exclusive with switch, augment, discontinuation, but a sub-group within LOT).
Interrupted treatment duration	Continuous: days Time from index medication to treatment discontinuation for those within treatment interruptions (>30 day gaps). Represents the time between index and end of last treatment, including any treatment gaps.

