	
77315 complex (mantle or inverted Y, tangential ports, the use of wedges, compensators, complex blocking, rotational beam, or special beam considerations).
 
77326 Brachytherapy isodose plan; simple (calculation made from single plane, 1 to 4 sources/ribbon application, remote afterloading brachytherapy, 1 to 8 sources).
 
77327 intermediate (multiplane dosage calculations, application involving 5 to 10 sources/ribbons, remote afterloading brachytherapy, 9 to 12 sources).
 
77328 complex (multiplane isodose plan, volume implant calculations, over 10 sources/ribbons used, special spatial reconstruction, remote afterloading brachytherapy, over 12 sources).
 
77403 Radiation treatment delivery, single treatment area, single port or parallel opposed ports, simple blocks or no blocks; 6-10 MeV.
 
77404 11-19 MeV.
 
77406 20 MeV or greater.
 
77408 Radiation treatment delivery, 2 separate treatment areas, 3 or more ports on a single treatment area, use of multiple blocks; 6-10 MeV.
 
77409 11-19 MeV.
 
77411 20 MeV or greater.
 
77413 Radiation treatment delivery, 3 or more separate treatment areas, custom blocking, tangential ports, wedges, rotational beam, compensators, electron beam; 6-10 MeV.
 
77414 11-19 MeV.
 
77416 20 MeV or greater.
 
77418 Intensity modulated treatment delivery, single or multiple fields/arcs, via narrow spatially and temporally modulated beams, binary, dynamic MLC, per treatment session.
 
77421 Stereoscopic X-ray guidance for localization of target volume for the delivery of radiation therapy.

PFIZER CONFIDENTIAL

Variable	Operational definition
Location of metastasis	
Categorical: by location (% of patients for each):
 

 Lymph nodes (ICD9-196.xx, ICD10 – C77)
 Lung (ICD9-197.0x, ICD10-C78.00)
 Liver (ICD9-197.7x, ICD10-C78.7)
 Brain (ICD9-198.3x, ICD10-C79.31)
 Bones (ICD9-198.5x, ICD10-79.5x)
 Adrenal gland (ICD9-198.7x, ICD10-79.7)
 Other (ICD9 196.xx-199.xx and ICD10 C77-C80 exclusive of above categories)

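### Table 6 counts kidney-coded secondaries (198.0/C79.0), which the entry criterion excepts, and C80 as 'Other' metastases; Table 5 leaves open whether kidney-coded secondaries can start the metastatic clock

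*Combined protocol and SAP*

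**What the plan says.** **Entry (Section 6.2.1).** Patients need "2 or more code for secondary malignancy codes indicating possible diagnoses for metastatic disease at least 30 days apart", between one year before and 30 days after index. The range is "ICD-9: xx-199.xx; ICD-10: C77-C79", with a named carve-out: "except ICD9: 198.0 Secondary malignant neoplasm of the kidney and ICD10: C79.0 Secondary malignant neoplasm of the kidney and renal pelvis".

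**Baseline site (Section 6.3.2, Table 6, Location of metastasis).** Six sites have their own codes: lymph nodes, lung, liver, brain, bones and adrenal gland. The seventh row is "Other (ICD9 196.xx-199.xx and ICD10 C77-C80 exclusive of above categories". Each row is reported as a percentage of patients. Under Analysis 2 in Section 6.1 the item is listed as "Secondary malignancy locations (6 months prior".

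**Time to first line (Section 6.3.1, Table 5).** The interval runs "from the first mRCC diagnosis (first ever secondary malignancy code associated with RCC) to first line therapy prescription". Analysis 1 in Section 6.1 describes the same metric as "Time from first ever metastatic diagnosis to first line regimen". Neither place lists codes or points back to 6.2.1.

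**Status of these cells.** Section 6.7 says that no separate SAP is required, and Section 6.8 says that analyses are programmed from the protocol's specifications.

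**The concern.** One code has different standing in different parts of the plan. A 198.0 or C79.0 claim does not count as evidence of metastasis at entry, but it counts as a metastatic site at baseline. Depending on how Table 5 is read, it may also date the first metastatic diagnosis. The carve-out looks deliberate: Section 6.1 says that the relationships between secondary malignancy, RCC and other cancer codes were explored when the criteria were built. The plan gives no reason for dropping it in Table 6.

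Two descriptors are at stake in a study that is wholly descriptive. Site of metastasis is one of the few clinical features by which the regimen cohorts are characterised. Time from metastatic diagnosis to first line is a listed Analysis 1 metric. Section 6.4 also plans to replicate results across databases to validate them. If the clock were programmed on different readings in different databases, part of any difference between them would be an artefact.

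**Working it through.** The plan states no figure on this point, so there is nothing to reproduce. The check has three steps.

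**1. Classify the codes under both rules.** Two reading assumptions are needed. The lower end of the ICD-9 entry range, printed only as xx, is taken as 196. The bone and adrenal ICD-10 codes in Table 6, printed without their letter, are taken as C79.5x and C79.7.

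| Code | Counts for entry (6.2.1)? | Row in Table 6 |
|---|---|---|
| 198.0 | No, excepted by name | Other |
| C79.0 | No, excepted by name | Other |
| C80 | No, outside C77-C79 but not named | Other |
| 199.0, 199.1 | Yes | Other |
| 197.7 / C78.7 | Yes | Liver |
| 198.7 / C79.7 | Yes | Adrenal gland |

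The conflict is explicit for 198.0 and C79.0. At the top of the range the mismatch is on the ICD-10 side only: both rules run to 199.xx in ICD-9, but entry stops at C79 while Table 6 goes on to C80.

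**2. Effect on 'Other'.** Adding codes to a category can only raise its percentage or leave it unchanged. A patient is misplaced only if 198.0, C79.0 or C80 falls in the 6-month look-back and is that patient's only 'Other' code. Let p be the share with another 'Other' code, and q the share of the remaining patients who have only these codes. Then

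reported Other = p + (1 − p)q, and the excess is (1 − p)q.

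Neither p nor q is in the documents. The values below are assumed.

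| p | q = 2% | q = 5% | q = 10% | q = 20% |
|---|---|---|---|---|
| 10% | 11.8% | 14.5% | 19.0% | 28.0% |
| 20% | 21.6% | 24.0% | 28.0% | 36.0% |
| 30% | 31.4% | 33.5% | 37.0% | 44.0% |

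For example, with p = 20% and q = 5%: 0.20 + 0.80 × 0.05 = 0.24, an excess of 4 percentage points.

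**3. Effect on the clock.** The interval is the index date minus the date of the first code. A wider code set can only move a first-ever date earlier or leave it unchanged. Take a constructed patient with C79.0 at day −300 and C78 codes at days −40 and −5. The two C78 codes are 35 days apart and inside the entry window, so the patient qualifies. If Table 5 takes any secondary malignancy code, the interval is 300 days. If it takes the 6.2.1 list, it is 40 days, a difference of 260. The two effects are separate: a C79.0 at day −300 lies outside the 6-month look-back, so it would not put this patient in 'Other'.

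**The case against.** The strongest case is that a strict list for admitting patients and a broader list for describing them can both be legitimate. Everyone in the cohort already has two qualifying codes, so what may be misclassified is the site and not metastatic status. Section 6.2.1 gives no reason for its carve-out, and a kidney-coded secondary could be genuine. A redacted item follows the entry criterion and may bear on this. The programming plan mentioned in Section 6.8 could settle the lists. All of this limits the consequence. It does not remove the conflict, because Table 6 states its own range and its own exclusions, and the plan nowhere says that the lists are meant to differ.

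A reader might infer more than the documents support:

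- **That Table 5 uses the excepted codes.** It lists none. Its wording, "first ever secondary malignancy code associated with RCC", can be read to include 198.0/C79.0, because 6.2.1 itself titles them secondary neoplasms. But it defines the first mRCC diagnosis, and a programmer could as well apply the entry list. For C80 the support is weaker still.
- **That C80 is ruled out as metastasis.** It is omitted from the entry range and not excepted by name. Entry accepts ICD-9 199.xx, and Table 6 pairs 199.xx with C80 at the top of its ranges. Nothing shows which section has the intended end point.
- **That 'Other' is known to be overstated, or by how much.** Only patients with no other code in that row are affected, and no frequencies are given.
- **That the number of metastatic sites is inflated.** No site count is defined.

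**Conclusion.** The point holds for Table 6. As written, 'Other' includes two codes that the entry criterion expressly excepts and one that lies outside its ICD-10 range. Any resulting error in the percentage is upward, and its size cannot be determined from the documents. The figures above show only how the excess would scale under assumed shares.

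For Table 5 the finding is an ambiguity. On one literal reading the clock can start too early; on the other it does not. The 260-day gap shows what can happen to one patient and is not an estimate for the cohort.

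Who enters the cohort on account of 198.0/C79.0 is not affected, and the plan specifies no outcome or model that uses the 'Other' row. This is a modest inconsistency in two descriptors. It is worth correcting because, without a separate SAP, these cells are the working specification.

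**What to change.** - Use one metastatic code list, the 6.2.1 list with its 198.0/C79.0 exception, for the 'Other' row in Table 6 and for the date of first mRCC diagnosis in Table 5. Refer to it by section in both tables.
- Give ICD-9 199.xx and ICD-10 C80 each the same status in 6.2.1 and Table 6, and state it. Dropping C80 from Table 6 leaves entry untouched. Adding it to 6.2.1 could widen the cohort.
- If kidney-coded secondaries are still of interest, report 198.0/C79.0 on a separate row of the site table.

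The cost is a few short text edits, with no new data. The downside is that the 'Other' percentage may fall, and genuine kidney-coded secondaries would no longer count there; the separate row keeps them visible. The size of the problem can be found in each database by counting patients whose only 'Other' code is 198.0, C79.0 or C80, and patients whose earliest secondary code is 198.0 or C79.0.

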6.3.3. Outcomes Variables

Table 7. Outcomes Variables

Variable	Operational definition
Days to Treatment Failure (TTF)	Time to treatment failure (TTF) is defined as the time from therapy start to treatment discontinuation for any reason, including switched, augmented therapy, end of enrollment, death.
Discontinuation	% discontinuing – those with gap in therapy greater than 30 days and who do not begin a new treatment.
Switching	% switching – those with gap in therapy greater than 30 days and who begin a new treatment.
Augmentation	% augmenting – those who begin a new treatment but continue using the original treatment (have an additional administration or refill) and do not have a gap in therapy greater than 30 days of their original treatment.
% Survived 3,6, 12 months	Mean/Median Survival Time (Days): Survival time will be described over 3,6, 12 months given follow-up time available in the data. Overall survival is defined as the length of time from index date of RCC diagnosis to patient death (or index date associated with FL Tx?) or end of available data for with no death indication. Overall landmark survival: described and compared over follow-up time periods (3,6, 12 months). Percentage of patients alive at 3,6, 12 months.
Overall Survival Time	Continuous: days Overall survival is defined as the length of time from index date of RCC diagnosis to patient death (or index date associated with FL Tx?)

PFIZER CONFIDENTIAL

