	
3. Analyze Select Outcomes of Interest:
 
• Time to Treatment Failure (TTF) - the time from therapy start to treatment discontinuation or therapy change (next line of therapy – switch or augment), end of enrollment, or death;• Treatment Interruption – those with gaps in treatment greater than allowable gap but who restart the same medication with no indication of switching or augmentation;• Health Care Costs (inpatient, outpatient, pharmacy, other);• Health Care Utilization (inpatient hospitalizations, ER, outpatient visits);• Survival Time and Landmark Survival. Mean/median survival time and % of population surviving 3, 6, and 12 months will be explored, although regimens are too new for extensive follow-up time. (Note: survival analysis will only be available in the Optum Clininformatics Database).
	
PPD [REDACTED], PharmD, MSc Director, PPD [REDACTED] [REDACTED] New York, NY 10017 Email: PPD [REDACTED]
 
PPD [REDACTED] Sr. Director, PPD [REDACTED] [REDACTED] Rockland, MA 02370 Email: PPD [REDACTED]
 
PPD [REDACTED], MD Title Address Email: PPD [REDACTED]
 
PPD [REDACTED] Executive Director, PPD [REDACTED] [REDACTED] New York, NY 10017 Email: PPD [REDACTED]

PFIZER CONFIDENTIAL

[REDACTED]

	PPD [REDACTED], MPH Director, PPD [REDACTED] New York, NY 10017 Email: PPD [REDACTED]
	PPD [REDACTED], MPH Manager, PPD [REDACTED] New York, NY 10017 Email: PPD [REDACTED]
	PPD [REDACTED] Intern, PPD PPD New York, NY 10017 Email: PPD [REDACTED]

PFIZER CONFIDENTIAL

[REDACTED]

TABLE OF CONTENTS

[figure not shown]
[figure not shown]
1. LIST OF ABBREVIATIONS.....	7
2. RESPONSIBLE PARTIES.....	9
3. AMENDMENTS AND UPDATES.....	10
4. RATIONALE AND BACKGROUND.....	10
5. RESEARCH QUESTION AND OBJECTIVES	11
6. RESEARCH METHODS	12
6.1. Study Design	12
6.2. Setting.....	17
6.2.1. Inclusion Criteria	17
6.2.2. Exclusion Criteria	18
6.3. Variables.....	19
6.3.1. Treatment Pattern Variables	19
6.3.2. Baseline Variables	21
6.3.3. Outcomes Variables.....	26
6.3.4. Cost and Utilization Variables.....	27
6.4. Data Sources.....	30
6.5. Study Size.....	33
6.6. Data Management	33
6.6.1. Record Retention	33
6.7. Data Analysis	34
6.8. Quality Control.....	35
6.9. Limitations of the Research Methods.....	35
6.10. Other Aspects	35
7. PROTECTION OF HUMAN SUBJECTS	35
7.1. Patient Information.....	35
7.2. Patient Consent.....	35
7.3. Institutional Review Board (IRB)/Independent Ethics Committee (IEC)	35

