6.1. Study Design

Patients receiving aRCC treatment (see [Table 4](#)), between April 2018 and the present, who have no prior aRCC treatment in their claims history will be identified for this study. The index date for each analysis will be defined as the date of initiation of the aRCC treatment. Patients must have at least 2 RCC diagnoses at least 30 days apart to be included. Patients must also have 2 secondary malignancy ICD9 or ICD10 codes (often used in claims data to suggest cancer metastases) at least 30 days apart in the 12 months pre and one month post index aRCC treatment. [CCI](#)

Various algorithms and temporal relationships between the secondary malignancy codes, RCC diagnosis codes and other cancer codes were explored toward developing the criteria for metastatic advanced RCC for this study.

Study will require a minimum of 12 months of enrollment prior to the index date. Feasibility was assessed for various lengths of continuous enrollment criteria (3, 6 and 12 months post index date) toward understanding sample sizes available for analysis and follow-up periods. Study outcomes will be assessed for three patient cohorts (3, 6 and 12 month cohorts) according to their available months of continuous enrollment.

PFIZER CONFIDENTIAL

First line therapy cohorts will first be presented for all patients regardless of follow-up time available. Baseline characteristics, costs and utilization will be measured over the 6 months prior to the index date. Duration of therapy and utilization analysis will require at least 6 months of post-index enrollment, with sub-analysis preformed on the cohorts with 3-months and 12-months of post-index enrollment. Utilization and cost will be performed per-utilizer-per-month (PUPM), and then separately for each of the cohorts with 3-month, 6-month and 12-months of post-index enrollment.

The analysis will focus on, but is not limited to, the following regimens:

- a. **Combo IO:** nivolumab combined with ipilimumab;
- b. **Monotherapy TKI:** sunitinib, cabozantinib, and pazopanib;
- c. **Combo TKI + IO:** avelumab in combination with axitinib, pembrolizumab in combination with axitinib;
- d. **Other:** all others regimens.

PFIZER CONFIDENTIAL

[figure not shown]
[figure not shown]
[figure not shown]

Figure 1: Cohort Identification

Analysis 1. Treatment Patterns and Duration

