- **% continuing** – those with no gap in therapy greater than 30 days and who do not begin a new treatment during the study period.
- **% discontinuing** – those with gap in therapy greater than 30 days and who do not begin a new treatment.
- **% with treatment interruption** - those with gap in therapy greater than 30 days but who eventually continue the original treatment (have an additional administration or refill) and do not switch or augment therapy during the study period.
- **% switching** – those with gap in therapy greater than 30 days and who begin a new treatment.
- **% augmenting** – those who begin a new treatment but continue using the original treatment (have an additional administration or refill) and do not have a gap in therapy greater than 30 days of their original treatment.
- **Overall and aRCC Follow-Up Costs:** Total and RCC-specific pharmacy, medical costs from aRCC therapy index through follow-up period (costs summarized as: mean, median costs per patient and costs per patient per month).

PFIZER CONFIDENTIAL

- **Overall and aRCC Follow-Up Utilization:** Total and RCC-specific inpatient, ER, outpatient visits from aRCC therapy index through follow-up period (utilization will be summarized as: mean, median utilization per patient and utilization per patient per month).
- **Overall landmark survival:** Using Optum claims and PanTher data, landmark survival will be described and compared over follow-up time periods (3, 6, 12 months).
- **Mean/Median Survival:** Using Optum claims and PanTher data median survival time will be described and compared over follow-up time periods determined after feasibility assessments of cohorts of interest.

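### End of enrollment is listed as a time-to-treatment-failure endpoint, and no censoring rule is stated for patients still on therapy

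*Combined protocol and SAP*

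**What the plan says.** Two places make end of enrollment an instance of discontinuation. Table 7 in Section 6.3.3 and the Analysis 3 outcome list in Section 6.1 both define TTF as time to "treatment discontinuation for any reason, including switched, augmented therapy, end of enrollment, death".

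The synopsis and Section 5 word it differently. They list it as a further endpoint beside discontinuation: "switch or augment), end of enrollment, or death".

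Table 5 in Section 6.3.1 defines the discontinuation date that TTF uses. It is the earliest of several dates, and the last two items are death and end of enrollment. No item is marked as an event or as censoring.

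Section 6.1 also defines status percentages. Continuing patients are "those with no gap in therapy greater than 30 days and who do not begin a new treatment during the study period"; discontinuing patients are "those with gap in therapy greater than 30 days and who do not begin a new treatment".

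On follow-up, Section 6.1 says: "Duration of therapy and utilization analysis will require at least 6 months of post-index enrollment". Outcomes follow-up runs to "the end of specified follow up period of 6 months, end of enrollment, or death", with provision for "subanalysis using 1-year or 2-years of follow-up time from study index date". The treated-period follow-up in the same section has no 6-month cap.

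Section 6.7 plans Kaplan-Meier curves for duration of therapy and survival, and says no separate SAP is needed. Section 6.8 has the analyses programmed from the protocol.

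**The concern.** End of enrollment is normally a reason to stop observing a patient, not a treatment failure. As written, the same patient can be continuing in one outcome and failed in another. Nothing in the supplied text resolves this for TTF. The nearest wording is in Table 7 for overall survival, which gives an end date for patients with no recorded death; it does not extend to TTF.

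TTF is the first-listed outcome, and Analysis 3 uses these outcomes to show unmet need under current therapies. Counting an administrative end as a failure can shorten TTF but never lengthen it. Two programmers working from this text could also code the same patient differently.

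**Working it through.** The plan gives no event count, expected TTF or data cut, so there is no figure of its own to reproduce. The check is textual first, then illustrative.

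**1. One patient through the definitions.** Take a patient on first-line therapy with no gap over 30 days and no new drug when enrollment ends.
- Section 6.1 percentages: continuing. Not discontinuing, because that needs a gap over 30 days.
- Table 5 date: end of enrollment, if it is the earliest item.
- TTF in Section 6.1 and Table 7: endpoint reached on that date.

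Now take the same patient still on therapy and still enrolled when the 6-month window closes. End of window is not in the TTF list, so there is neither an event nor a censoring rule.

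**2. Main 6-month window.** With at least 6 months of enrollment required, end of enrollment cannot precede the end of the window. The open question is how many patients have no rule. Assume exponential TTF with true median m months. The share still on therapy at w months is 2^(−w/m).
- w = 6: m = 6 gives 2^(−1) = 0.50; m = 10 gives 2^(−0.6) = 0.66.
- For the 3- and 12-month cohorts the shares are 0.71 and 0.25 (m = 6), and 0.81 and 0.44 (m = 10).

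**3. Uncapped follow-up.** Three further assumptions are needed: follow-up is not cut at 6 months, the data cut is coded as end of enrollment, and index dates are uniform over the window in Section 6.2.1 ("recorded in the database between April 2018-March 31, 2019"). If data end D months after that window closes, follow-up is uniform on (D, D+12). Coding its end as an event, the curve estimates

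S(t) × G(t), with S(t) = 2^(−t/m), and G(t) = (D + 12 − t)/12 for t between D and D + 12 (G = 1 before D).

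The reported median solves S(t)G(t) = 0.5. The share of endpoints that are only end of follow-up is the mean of 2^(−c/m) over c from D to D+12.

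A cut near the protocol date of 4 October 2019 gives D = 6, so follow-up of 6 to 18 months:

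| True median (months) | Reported median | Endpoints that are end of follow-up |
|---|---|---|
| 6 | 6.0 | 27% |
| 10 | 7.7 | 45% |
| 15 | 8.9 | 58% |

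Check for m = 10 at t = 7.74: 2^(−0.774) = 0.585; (18 − 7.74)/12 = 0.855; product 0.500.

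**4. Range over the unknown cut.** For D = 3, 6 and 9, a true median of 12 appears as 6.3, 8.3 and 10.2 months, and a true median of 6 as 4.7, 6.0 and 6.0. Bias appears only when the true median exceeds minimum follow-up, D. In simulation at D = 6, censoring instead gave a Kaplan-Meier median of 11.9 for a true 12.

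**The case against.** The strongest reply is that the main analysis shows no biased median. Section 6.1 requires 6 months of enrollment and sets a 6-month outcomes window, so end of enrollment never comes first. That stands: what is left there is a missing rule, not a demonstrated bias.

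The bias in step 3 also depends on coding. Table 5 lists end of enrollment and end of data availability as separate final statuses, and Section 6.2.1 requires enrollment through the available data. A survivor's follow-up may therefore end as end of data, which the TTF list omits. This stands too; it replaces a wrong rule with no rule.

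A third reply is that Kaplan-Meier implies censoring. That is probably the intention, but the method needs an event indicator, and the only written list puts end of enrollment with the failures.

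Some stronger readings are tempting but unsupported:
- A reader might infer that the plan contradicts itself on follow-up length. Section 6.1 makes 6 months the main requirement with 3 and 12 months as sub-analyses, and allows longer sub-analyses. The 24 months in Section 6.4 is a data window in a source description.
- A reader might infer that TTF will be reported as simple means of truncated times. Section 6.7 names Kaplan-Meier for duration of therapy, and that specific sentence plausibly governs.
- A reader might infer distorted differences between regimens. Follow-up by regimen is not given, so neither direction nor size can be stated.

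**Conclusion.** The point holds as a defect in the written definition. Section 6.1, Table 7 and the Table 5 date rule treat end of enrollment as discontinuation; the synopsis and Section 5 list it as an endpoint; no section censors TTF. Confidence in that textual finding is high.

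Its numerical effect is conditional. In the main window it is an unstated rule for the patients still on therapy at 6 months. A downward bias in the median needs uncapped follow-up, the data cut coded as end of enrollment, and a true median above minimum follow-up. The medians in the working rest on assumed cuts, exponential TTF and uniform indexing, and are not predictions. The percentages continuing, discontinuing, switching and augmenting are unaffected. The study is descriptive, so this should be fixed but does not undermine the design.

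**What to change.** 1. Remove end of enrollment from the TTF event list in the synopsis, Section 5, Section 6.1 (Analysis 3) and Table 7. Label it a censoring date in Table 5.
2. Add to Section 6.7: the TTF event is the earliest of discontinuation, switch, augmentation or death. Discontinuation means a gap over 30 days as in Section 6.1 and Table 7, dated by the Table 5 run-out or last-administration rule without its end-of-enrollment item. A bare reference to discontinuation as defined in the protocol would not do, because Table 5 itself contains end of enrollment. Otherwise censor at the earliest of end of enrollment, end of data or end of the stated follow-up window.
3. State whether an interruption followed by resumption is a TTF event. Section 6.1 excludes patients who switch or augment from that category, while Table 5 lets it overlap with switching, augmentation and discontinuation; the two need reconciling.
4. Confirm Kaplan-Meier as the TTF summary and report the number censored per regimen.
5. Add a limitation: in databases without death data, a death on therapy may be censored at disenrollment and may lengthen TTF.

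The cost is wording in four places, one Table 5 label, a few sentences in Section 6.7 and a censoring flag in the program. Some medians may not be reached.
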